Cognizant of these findings, we explored whether self-efficacy was affected by our breathing technique in 64 COPD patients undergoing rehabilitation.⁵ In that study, self-efficacy (quantified in terms of mastery over breathing) was greater after exercise-training plus breathing-retraining than after exercise-training alone.⁵ This observation raises the possibility that COPD patients undergoing rehabilitation programs where breathing-retraining is combined to traditional exercise-training may maintain the beneficial effects of rehabilitation for a longer time than patients undergoing traditional exercise alone. Accordingly, we propose to test the hypothesis that in COPD patients, improvements in exercise duration on a constant-load treadmill test will be greater after completing 12-weeks of breathing-retraining plus treadmill exercise followed by a 42-week adherence-intervention program (one year total) than after completing 12-weeks of treadmill exercise alone followed by a 42-week adherence-intervention program. The adherence-intervention will consist of weekly phone calls and monthly 'booster' visits to reinforce both exercise and, for the breathing-retraining group, breathing training. In addition, we propose to study potential mechanisms that can affect long-term sustainability of the gains achieved through pulmonary rehabilitation.

Hypothesis/Research Questions

Primary

H₁ In patients with COPD, improvements in exercise duration on a constant-load treadmill test will be greater after completing 12 weeks of breathing-retraining plus treadmill exercise-training followed by a 42-week adherence-intervention program (one year total) than after completing 12 weeks of treadmill exercise-training alone followed by a 42-week adherence-intervention program (one year total).

Secondary

H₂ One year after randomization, reductions in exercise-induced dynamic hyperinflation during a constant-load treadmill test will be greater in the breathing-retraining group than in the exercise-alone group.

H₃ One year after randomization, improvements in the 6-minute walk distance will be greater in the breathing-retraining group than in the exercise-alone group.

H₄ One year after randomization, improvements in perceived mastery over breathing will be greater in the breathing-retraining group than in the exercise-alone group.

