Recruitment. Patients with moderate-to-severe COPD, ≥ 40 years of age, will be recruited from the outpatient Pulmonary Medicine Service at the Hines VA (**Table 1**). No patient will be excluded based on gender or ethnicity. About 9 patients per month will be ‘enrolled’ with 5 of them being ‘randomized’.

Screening and Baseline

Testing. Proposed study participants will be screened for eligibility and written informed consent will be obtained. All testing and training will take place at Hines VAH’s Physical Performance Research Laboratory. During screening, patients will be asked about their medical history and medication use. This will be followed by physical examination, pulmonary function testing and completion of quality of life/dyspnea questionnaires. Then, patients will undergo an incremental-load

Table 1. Study Inclusion and Exclusion Criteria

Inclusion Criteria	Exclusion Criteria

 ≥ 40 yr of age FEV₁ $\leq 70\%$ FEV₁/FVC $< 70\%$ RV/TLC $\geq 120\%$ mean SpO₂ $\geq 90\%$ at peak exercise (w/ or w/o O₂) Inspiratory capacity decline of $>0.15L$ from rest to peak exercise 	
 Respiratory infection/exacerbation within the previous four weeks Exercise limiting heart disease (+ stress test or other indicators of heart disease or complaints of angina during the stress test) Primary asthma Congestive heart failure (New York Heart Association Class III or IV) Exercise-limiting peripheral arterial disease (stops exercise due to intermittent claudication) Stops exercise due to arthritic pain in the knee or hips (self-report) Inability to walk on the treadmill Pregnancy Any unforeseen illness or disability that would preclude exercise testing or training Participation in a formal exercise program within the previous 12 weeks

treadmill test. Thereafter, eligible patients will perform the baseline tests⁷ that include two constant-load treadmill tests, functional assessment of the respiratory muscles and quadriceps, quadriceps ultrasonography, physical activity monitoring and 6-min walk test. After the baseline testing is completed and study criteria are met, patients will be randomized to breathing-retraining plus exercise-training or to exercise-training alone.

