Incremental-Load Treadmill Test. The purpose for this test is to determine the patient's VO_{2peak} and his/her breathing pattern during exercise. This information will be used to set the workload during the constant-load treadmill test and to set the breathing-retraining goals during exercise-training. At the start of the incremental-load test the treadmill will be set at 0% grade and at a speed of 1.8 mph. Every 30 seconds during testing, the incline will increase by 0.5%. Additionally, after minute 6 of the protocol, the treadmill's speed will increase by 0.2 mph every 3 min. With this protocol, energy demands step up by one metabolic equivalent (MET)⁹⁴ every 3 min.

Constant-Load Treadmill Test. The purpose of this test is to determine exercise duration, respiratory pattern, extent of exercise-induced dynamic hyperinflation, dyspnea and leg fatigue at randomization, after 12-weeks of training and 6 and 12 months after randomization. The speed and grade of the treadmill will be the same as the speed and grade recorded when patients reached 85% of their VO_{2peak} during the baseline incremental-load treadmill test.

Recordings During Incremental-Load and Constant-Load Tests. During all treadmill tests, cardiac activity (Leads II, V1, and V5; General Electric), SpO_2 (Nellcor Works), airflow (MedGraphics). VO_2 and VCO_2 (MedGraphics) will be monitored continuously. This setup allows us to record of minute ventilation, tidal volume, and respiration rate as well as breath-by-breath recordings of gas exchange.

As previously described,^{6,7,84} VO_{2peak} will be the highest value of VO_2 recorded between the 60 sec before and 30 sec after the incremental-load treadmill exercise test ends, when patients have reached their 'peak effort'.

Inspiratory capacity will be measured just before each exercise test, every 2 min throughout the test, at peak exercise and at 2 and 4 min into recovery.⁷ Similarly, blood pressure will be recorded every 2 min. Ratings of perceived dyspnea and exertion will be obtained using Borg's ratio scale^{49,50} during the last 30 sec of each stage of exercise. For patients experiencing exercise desaturation ($SpO_2 < 90\%$), an oxygen reservoir system (100 L Douglas bag) will be used for continuous oxygen supplementation.⁷

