The principal analysis of the primary outcome measure will compare changes in duration of exercise from baseline to end of follow-up in the constant-load treadmill test using the 2-sample t-test (two-tailed $P = .05$). The primary analysis will be based on intention-to-treat principles (i.e., all randomized patients will be included in the analysis). Multiple imputation will be used for study patients who are missing the 12-month measurement. This imputation model will be based on the baseline characteristics of the study participants. The primary analysis will be repeated, restricted to patients who complete the treatment protocol. Linear regression will be used to determine whether the observed treatment persists after adjustment for baseline covariates and measures of treatment adherence. Since several measurements will be taken on each patient, mixed-models analysis will be used to compare the changes on the constant-load treadmill test over time between the two groups. The missing data pattern will be explored to determine whether data have been informatively censored. If the data do not appear to be missing at random, an indicator variable (alone and as an interaction with slope) will be used in the model to separately estimate intercepts and slopes for the censored group and the group with complete data. At the patient level, random intercepts and slopes will be assumed. Several correlation structures will be evaluated to determine which best represents the observed correlation structure. We will also use multiple imputation to estimate the missing values in the mixed-model ANOVA as a sensitivity analysis. This will be accomplished in two ways. The first multiple imputation technique will account for the treatment group to which each study participant was randomized. We will then use a second multiple imputation model in which all missing values are imputed from a model that only includes data from the control group. This latter multiple imputation model will provide a lower bound (or conservative) estimate of the treatment differences.

Secondary Hypotheses:

H₂: ONE YEAR AFTER RANDOMIZATION, REDUCTIONS IN EXERCISE-INDUCED DYNAMIC HYPERINFLATION WILL BE GREATER IN THE BREATHING-RETRAINING GROUP THAN IN THE EXERCISE-ALONE GROUP.

Statistical analysis for H₂ will parallel that of H₁.

H₃: ONE YEAR AFTER RANDOMIZATION, IMPROVEMENTS IN THE 6-MINUTE WALK DISTANCE WILL BE GREATER IN THE BREATHING-RETRAINING GROUP THAN IN THE EXERCISE-ALONE GROUP.

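### H2 fixes neither the variable nor the time point for dynamic hyperinflation; read at end-exercise, it could shrink, hide or reverse a real benefit

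*Combined protocol and SAP*

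**What the plan says.** All references are to the combined protocol and SAP.

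- **Hypothesis/Research Questions, Secondary.** For the 12-month assessment, H2 states: "reductions in exercise-induced dynamic hyperinflation during a constant-load treadmill test will be greater in the breathing-retraining group". The comparator is exercise training without breathing-retraining. No variable or time within the test is named.
- **Statistical Analysis, Secondary Hypotheses.** The whole analysis is "Statistical analysis for H₂ will parallel that of H₁". For H1, the plan is to "compare changes in duration of exercise from baseline to end of follow-up in the constant-load treadmill test using the 2-sample t-test".
- **Constant-Load Treadmill Test.** One purpose of the test is to determine the "extent of exercise-induced dynamic hyperinflation, dyspnea and leg fatigue at randomization, after 12-weeks of training and 6 and 12 months after randomization". It does not say when in the test that extent is read. The workload is fixed from baseline: "The speed and grade of the treadmill will be the same as the speed and grade recorded when patients reached 85" per cent of peak oxygen uptake in the baseline incremental test.
- **Recordings During Incremental-Load and Constant-Load Tests.** IC is measured before each test, then "every 2 min throughout the test, at peak exercise and at 2 and 4 min into recovery".
- **Table 1.** The inclusion criterion "Inspiratory capacity decline of $>0.15L$ from rest to peak exercise" is the only place where hyperinflation is given a measurable form.
- **Sample Size Calculation.** The arms are expected to differ by 8.27 min in exercise duration at 12 months (pooled SD 13.7 min).
- **Screening and Baseline Testing.** There are two baseline constant-load tests.

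**The concern.** Dynamic hyperinflation builds up during exercise, so its size depends on when it is read. At a fixed workload, the arm that walks longer has its end-exercise IC read later. H1 predicts that this will be the breathing-retraining arm and that treatment is the cause. An end-exercise contrast would then mix two effects: slower hyperinflation, which H2 is about, and a longer time in which to hyperinflate, which follows from H1. The more strongly H1 holds, the harder it becomes for H2 to show a benefit.

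H2 is the mechanistic hypothesis: the Introduction names exercise-induced dynamic hyperinflation as a major determinant of limited exercise tolerance. With nothing fixed in advance, the choice between an end-exercise and an equal-time reading could be made after the data are seen, and the two can differ in size or even in sign.

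**Working it through.** **1. The plan's own figure.** Effect size = 8.27/13.7 = 0.604. By the normal approximation, n per arm = 2 × (1.960 + 1.036)² / 0.604² ≈ 49.3, so 50. With 50 per arm, power is 0.855 (normal) or 0.848 (exact t). The stated 100 patients for 85% power is reproduced, so 8.27 min is the trial's own planning gap. H2 has no stated effect size, SD or power.

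**2. What must be assumed.** The documents give neither the control-arm duration at 12 months (call it T) nor the shape of the IC fall over time. Both are varied below, with the treated arm exercising T + 8.27 min. Baseline falls are equal in expectation under randomization, so the expected difference in change from baseline equals the difference in the 12-month falls.

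**3. IC falls linearly.** Let the control rate be r and the treated rate r(1 − d). The end-exercise falls are rT and r(1 − d)(T + 8.27). A benefit appears only if d > 8.27/(T + 8.27). For a true 30% slower rate, the ratio of treated to control end-exercise fall is 0.7(T + 8.27)/T.

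| T (min) | Slowing needed before any benefit shows | Treated/control fall, true 30% slowing |
|---|---|---|
| 10 | 8.27/18.27 = 45% | 1.28 |
| 15 | 8.27/23.27 = 36% | 1.09 |
| 20 | 8.27/28.27 = 29% | 0.99 |
| 30 | 8.27/38.27 = 22% | 0.89 |

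A real 30% slowing would look 28% worse at T = 10, about equal at T = 20, and 11% better at T = 30.

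**4. IC falls to a plateau.** Control fall at time t = 0.40 × (1 − e^(−t/τ)) L; treated plateau 30% lower (0.28 L). The table gives the end-exercise difference as a share of the difference at equal time T.

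| Time constant τ (min) | T = 10 | T = 20 | T = 30 |
|---|---|---|---|
| 2 | 98% | 100% | 100% |
| 5 | 70% | 96% | 100% |
| 10 | 24% | 79% | 93% |
| 20 | −22% | 54% | 77% |

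Example, τ = 10 and T = 10: control 0.253 L; treated at equal time 0.177 L (difference 0.076 L); treated at 18.27 min 0.235 L (difference 0.018 L); 0.018/0.076 = 24%.

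**5. Illustrative simulation.** 4,000 trials, 50 per arm, T = 15, true 25% benefit, IC measurement SD 0.12 L, durations truncated at 4 min; all these values are assumed. The equal-time reading is at 8 min, and patients who stop earlier contribute their end value.

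- Linear decline (0.030 against 0.0225 L/min, between-patient SD 0.010), duration SD 7 min. Without truncation the end-exercise falls are 0.030 × 15 = 0.45 L and 0.0225 × 23.27 = 0.52 L. The treated arm looks about 0.07 L worse and is significantly worse in about 21% of trials. At equal time it is about 0.05 L better, significant in about 38%.
- The same with the plan's pooled SD of 13.7 min: about 0.03 L worse at end-exercise, significantly worse in about 6%. At equal time it is about 0.04 L better, significant in about 26%.
- Early plateau (τ = 3 min, control plateau 0.45 L, between-patient SD 0.15), duration SD 7 min: the two readings agree, significant in about 71% (end-exercise) and 75% (equal time).

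**The case against.** A reader might infer that the plan commits H2 to an end-exercise comparison. It does not. Table 1 sets who may enter and does not link its criterion to H2. The description of the constant-load test speaks only of extent, and the IC schedule serves an equal-time reading as well as a peak one. What the documents support is an undefined outcome, not a chosen confounded contrast. This part of the objection stands.

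A reader might also infer that longer exercise will cancel the benefit. That requires IC to keep falling late in the test, and the documents give no time course. With a short time constant almost all of the effect is kept, and with a long control test most of it. The size of any reversal in simulation also depends on the duration SD. This stands too, so the masking is a possibility and not a forecast.

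Finally, this is one of three secondary hypotheses, and the readings needed for an equal-time analysis will exist in any case. That limits the severity. It does not remove the need to choose in advance, because the only measure the documents spell out points to peak exercise, equal time is never mentioned, and copying the H1 t-test adds nothing that accounts for exercise time.

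**Conclusion.** The concern holds as a gap in specification with a conditional consequence. H2 has no defined variable or time point. One natural reading, end-exercise IC, compares the arms after times planned to differ by 8.27 min because of treatment. If IC declines linearly, no benefit shows until the rate is more than 45%, 36%, 29% or 22% slower, for an assumed control duration of 10, 15, 20 or 30 min. If IC plateaus early, little is lost (98% to 100% kept with a time constant of 2 min and T of 10 min or more). In none of the scenarios worked here did the equal-time reading do worse than the end-exercise one. The plan should be changed, but this is an improvement to a secondary endpoint: H1 and the sample size are unaffected.

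**What to change.** In the H2 analysis, and before any outcome data are examined:

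1. Define the outcome as the fall in IC from rest at within-patient isotime: the last 2-minute reading reached in the baseline constant-load test, and the reading at the same minute in the follow-up test.
2. State which of the two baseline constant-load tests sets isotime.
3. If the follow-up test is shorter, use the last 2-minute reading common to both tests. If a test ends before 2 min, use its end value.
4. Compare arms on the follow-up isotime value with the baseline isotime value as covariate, in place of the t-test on change. Under randomization this estimates the same difference and makes use of the baseline reading.
5. Report the rest-to-peak change in IC as supportive, beside exercise duration, so that a reader can see how far the two readings diverge.

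The cost is SAP wording only: the readings are already scheduled and the workload is unchanged across visits. There are two small downsides. The fallback reading still depends partly on follow-up duration, which treatment may affect, so the number of patients using it should be reported by arm. Tests under 2 min have no intermediate reading to use.

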General Overview of Design. The proposed study has been designed as a randomized, controlled clinical trial. After completing baseline testing, patients will be randomized to one of two groups: breathing-retraining plus exercise-training or exercise-training alone. We did not include a non-treatment group as it has been clearly demonstrated that patients randomized to a non-treatment group (no exercise-training) experience no significant improvements in exercise capacity.^{12,16}

Sample Size Calculation. Sample size calculations for the current proposal are based on two considerations. First, in our previous investigation⁶ we observed that the mean exercise endurance 6 weeks after the completion of training was 7.0 min greater with exercise plus breathing-retraining than with exercise alone. When the analysis was restricted to those patients who developed exercise-induced dynamic hyperinflation, the difference was 8.27 min. Second, due to greater gains in mastery over breathing with exercise plus breathing-retraining than with exercise alone,⁴⁷ we expect that the difference in exercise endurance between the two groups will widen over time – i.e., we expect that the breathing-retraining group will better maintain the benefits of rehabilitation than the exercise-alone group. Based on these considerations we conservatively estimate that the difference in exercise duration between the groups at 12 months will be 8.27 minutes with a pooled standard deviation of 13.7 min (effect size = .60).

This means that to achieve 85% power, 100 patients are needed (50 in each group) using two-sample t-test ($\alpha = .05$).

According to the local IRB, enrollment is the equivalent to a patient signing an informed consent. In our three latest studies,^{6,7,84} 30-46% of patients who signed the informed consent (i.e., enrollees) did not meet PFT criteria or did not qualify for other reasons. Accordingly, to have complete data on 100 patients while accounting for attrition due to disqualifying conditions, lack of exercise-induced dynamic hyperinflation, and short-term and long-term attrition, we plan to ‘enroll’ 250 patients (i.e., signed informed consent) and to ‘randomize’ 140 of them.

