Chronic Respiratory Disease Questionnaire (CRQ). This questionnaire is designed to determine how the lives of patients with chronic airflow limitation are affected by the illness and the perceived impact of symptoms and limitations on quality of life.¹⁰⁵ The 20 questions on the CRQ measure four dimensions: dyspnea, fatigue, emotional function, and the patient's feeling of control over the disease (mastery). Each question is scored during a structured interview. Test-retest reliability and validity of the CRQ have been established.¹⁰⁶ Patients will not be informed of their previous responses on the questionnaire when the CRQ is administered at follow-up. CRQ scores will be used as covariates in the final analysis if appropriate.

Short Form-36 Health Survey (SF-36): This is a general health-related quality of life instrument to quantify perceived physical function and mental health.^{107,108} The SF-36 will be used to describe the sample and to have a comparator measure to published clinical pulmonary rehabilitation programs.¹⁰⁹

Charlson Comorbidity Index. This validated¹¹⁰ and widely utilized index^{65,66} will be used to determine whether comorbidities influence study outcomes.

Depression and Anxiety. To control for the influence of ongoing depression and anxiety on adherence, the Center for Epidemiologic Studies Depression Scale (CES-D)¹¹¹ and the State-Trait Anxiety Inventory (STAI)¹¹²⁻¹¹⁴ will be administered at baseline and at major data collection time-periods. CES-D and STAI scores will be used as covariates in the final analysis if appropriate.

Self-Efficacy. The Self-Efficacy for Walking¹¹⁵ and the Self-Efficacy for Shortness of Breath questionnaires¹¹⁶ will be used to measure self-efficacy at all time periods.^{115,117} These are reliable and valid¹¹⁶ instruments designed to assess a patient's confidence in keeping shortness of breath from interfering from walking or from doing what they want to do.

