Exacerbations. Approximately 50% of patients with moderate-severe COPD are expected to experience an exacerbation over the course of 12 months.¹⁵ Exacerbations negatively impact adherence to exercise programs and quality of life.¹⁵ Exacerbations will be monitored weekly throughout the study. Acute exacerbations are defined by changes in sputum color, volume or consistency and are accompanied by an increase in dyspnea.⁶⁰ Acute exacerbations are classified as mild (the need for increased use of inhaled bronchodilators only), moderate (the need for systemic corticosteroids and/or antibiotics), or severe (the need for hospitalization).⁶⁰ Since moderate exacerbations usually resolve in approximately two weeks,¹¹⁸

patients who experience an exacerbation within two weeks of testing will have their testing deferred until the exacerbation has resolved.

Statistical Analysis. Descriptive statistics will be used to summarize baseline characteristics of participants. Comparison of the two groups (breathing-retraining plus exercise-training and exercise-training alone) will be undertaken for all baseline variables to determine whether any imbalances on purported prognostic factors exist. T-test for two independent samples will be used for comparison of the two groups at baseline, continuous data and changes in continuous outcomes from baseline to end of treatment. The continuity-corrected chi-square test will be used to compare categorical data in the two groups at baseline and end of treatment. When this test is not appropriate due to small category frequencies, Fisher's exact test will be used. To examine the potential for response bias, baseline measurements of patients who complete and do not complete follow-up visits will be compared. This procedure will be done for the overall study sample and for each randomized group.

Primary Hypotheses:

H₁: IN PATIENTS WITH COPD, IMPROVEMENTS IN EXERCISE DURATION ON A CONSTANT-LOAD TREADMILL TEST WILL BE GREATER AFTER 12 WEEKS OF BREATHING-RETRAINING PLUS TREADMILL EXERCISE-TRAINING FOLLOWED BY A 42-WEEK ADHERENCE-INTERVENTION PROGRAM (ONE YEAR TOTAL) THAN AFTER 12 WEEKS OF TREADMILL EXERCISE-TRAINING ALONE FOLLOWED BY A 42-WEEK ADHERENCE-INTERVENTION PROGRAM (ONE YEAR TOTAL).

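### Adjust the primary analysis of H1 to H4 for the baseline value (ANCOVA), and put randomized arm in the primary imputation model

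*Combined protocol and SAP*

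**What the plan says.** Under Primary Hypotheses in the Statistical Analysis section, "The principal analysis of the primary outcome measure will compare changes in duration of exercise from baseline to end of follow-up" on the constant-load treadmill test, by two-sample t-test at two-sided 0.05, in all randomized patients. The general paragraph of that section likewise assigns the t-test to "changes in continuous outcomes from baseline to end of treatment". H2, H3 and H4 are each said to parallel H1.

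Missing 12-month values are multiply imputed, and for the primary analysis "This imputation model will be based on the baseline characteristics of the study participants". Treatment group is first named later, for a sensitivity analysis of the mixed model: "The first multiple imputation technique will account for the treatment group to which each study participant was randomized".

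Three other items come near to baseline adjustment:
- "Linear regression will be used to determine whether the observed treatment persists after adjustment for baseline covariates and measures of treatment adherence".
- "mixed-models analysis will be used to compare the changes on the constant-load treadmill test over time between the two groups".
- Under Depression and Anxiety, "CES-D and STAI scores will be used as covariates in the final analysis if appropriate"; CRQ scores are treated the same way.

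The Sample Size Calculation assumes that "the difference in exercise duration between the groups at 12 months will be 8.27 minutes with a pooled standard deviation of 13.7 min". It asks for 50 patients per group for 85% power, and plans 140 randomized to obtain 100 with complete data.

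**The concern.** A change score fixes the slope of the 12-month value on the baseline value at 1. ANCOVA estimates that slope, so it removes at least as much baseline variation. The baseline test is already collected, so whatever precision the fixed slope gives up could be had at almost no cost.

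None of the three nearby items fills the gap. The linear regression is supplementary and also adjusts for adherence, which arises after randomization. The mixed model is supplementary too. The questionnaire covariates are not fixed in advance. None makes the baseline value of the outcome a pre-specified covariate in the principal analysis.

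The imputation model belongs in the same amendment. If arm is left out, imputed patients in both groups are drawn from one common regression, which pulls the groups together. Changing only the test would leave that loss in place.

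**Working it through.** **Inputs from the document.** Difference 8.27 min; SD 13.7 min (not stated whether of 12-month values or of changes); two-sided 0.05; 50 completers per arm; 140 randomized, 100 complete.

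**Assumed, because the document gives neither.** Baseline to 12-month correlation rho from 0.3 to 0.7; r = baseline SD / 12-month SD from 0.5 to 1.0.

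**1. The plan's own figure.** d = 8.27/13.7 = 0.604. The normal-approximation formula gives 50 per group, as stated. Noncentral-t power at 50 per group (98 df) is 84.8%.

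**2. Variance comparison.** Write s0 and s1 for the baseline and 12-month SDs.
- Var(change) = s1² + s0² − 2·rho·s0·s1
- Var(ANCOVA) = s1²(1 − rho²)
- Difference = (s0 − rho·s1)², never negative, and zero only when rho = r (slope exactly 1).

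ANCOVA's cost is one degree of freedom (97 instead of 98) and a mean variance factor of 1 + 1/96 = 1.0104.

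**3. Power with 50 completers per arm.** ANCOVA power is averaged over chance baseline imbalance.

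If 13.7 is the 12-month SD: change SD = 13.7·√(1 + r² − 2·rho·r), and ANCOVA SD = 13.7·√(1 − rho²). For example, at r = 1.0 and rho = 0.3 these are 16.21 and 13.07.

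| Power (%), rho = | 0.3 | 0.4 | 0.5 | 0.6 | 0.7 |
|---|---|---|---|---|---|
| ANCOVA, any r | 87.6 | 90.0 | 93.0 | 96.0 | 98.6 |
| Change, r 1.0 | 71.4 | 77.9 | 84.8 | 91.6 | 97.1 |
| Change, r 0.8 | 79.2 | 84.8 | 90.3 | 95.2 | 98.6 |
| Change, r 0.6 | 84.8 | 89.0 | 92.9 | 96.2 | 98.6 |
| Change, r 0.5 | 86.6 | 90.0 | 93.2 | 96.0 | 98.1 |

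If 13.7 is the SD of change: the change score has 84.8% throughout, and ANCOVA SD = 13.7·√[(1 − rho²)/(1 + r² − 2·rho·r)].

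| Power (%), rho = | 0.3 | 0.4 | 0.5 | 0.6 | 0.7 |
|---|---|---|---|---|---|
| ANCOVA, r 1.0 | 95.8 | 94.4 | 93.0 | 91.4 | 89.7 |
| ANCOVA, r 0.8 | 91.9 | 90.0 | 88.2 | 86.5 | 85.1 |
| ANCOVA, r 0.6 | 87.6 | 86.1 | 84.9 | 84.4 | 85.1 |
| ANCOVA, r 0.5 | 85.9 | 84.9 | 84.4 | 85.0 | 87.0 |

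The largest gain is 16.2 points (12-month SD, r 1.0, rho 0.3). The largest loss is 0.37 points (SD of change, rho = r).

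**4. The imputation model.** 40 of 140 missing is 28.6%. With arm omitted, the expected difference is 8.27 × 100/140 = 5.91 min.

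This was simulated with 70 per arm and 20 per arm missing completely at random (the equal split is assumed). Data were bivariate normal, imputation was Bayesian linear from the baseline value with or without arm, and 20 imputations were combined by Rubin's rules. There were 10,000 trials per scenario, with Monte Carlo error at most 0.5 points. Mean estimates were 5.86 to 5.95 min with arm out and 8.23 to 8.32 min with arm in, under both analyses.

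| Power (%), change / ANCOVA | rho 0.3 | rho 0.5 | rho 0.7 |
|---|---|---|---|
| 12-month SD, r 1.0, arm in | 75.1 / 87.1 | 86.7 / 92.4 | 97.4 / 98.4 |
| 12-month SD, r 1.0, arm out | 46.6 / 65.2 | 62.5 / 75.7 | 86.4 / 92.0 |
| 12-month SD, r 0.5, arm in | 85.9 / 87.0 | 91.8 / 91.8 | 97.8 / 98.2 |
| 12-month SD, r 0.5, arm out | 62.9 / 64.1 | 75.6 / 75.1 | 89.8 / 91.9 |
| SD of change, r 1.0, arm in | 88.5 / 95.7 | 86.4 / 92.1 | 85.1 / 88.8 |
| SD of change, r 1.0, arm out | 63.7 / 82.8 | 63.0 / 76.0 | 61.3 / 68.4 |
| SD of change, r 0.5, arm in | 83.4 / 84.3 | 83.1 / 83.0 | 84.8 / 86.4 |
| SD of change, r 0.5, arm out | 59.5 / 61.2 | 59.9 / 59.8 | 61.0 / 64.2 |

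Under no effect (two scenarios), rejection was 4.8 to 5.1% with arm in and 0.7 to 1.8% with arm out. Omitting arm is conservative: it loses power and does not inflate type I error.

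**The case against.** The planned test is valid and matches the sample size calculation, so replacing it could be called preference. The gain cannot be fixed from the document. Each patient's treadmill load is set at 85% of his or her own baseline VO2peak, so baseline durations may vary less than 12-month durations, and the gain shrinks as r falls towards rho. Over an even grid of 198 combinations of SD reading, r and rho, the gain is at least 2 points in 49% and at least 5 in 27%. Restricted to r of 0.7 or less (90 combinations), the median gain is 0.3 points, with at least 2 points in 17% and at least 5 in one. These are shares of an assumed grid, not probabilities. The 16-point figure also needs 13.7 to be the 12-month SD; if it is the SD of change, the largest gain is 11.0 points. All of this stands, and it limits the size of the claim. It does not remove the asymmetry: at most 0.4 points lost against a possibly material gain, using data already collected.

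A second objection is that the imputation problem is separate, because it affects the t-test equally, and that the text does not expressly exclude arm. Both statements are correct. The wording is under-specified, but it names arm only for a sensitivity imputation, so the natural reading leaves arm out. The two changes are best made together because the first alone leaves the larger loss.

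A third is that the 12-week and 6-month treadmill tests could also inform the imputation. That is fair; their effect was not quantified here, and adding them does not conflict with the proposal.

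**Conclusion.** The point holds as an inexpensive improvement that should be made; it is not an error in the planned test or its sample size. With 50 completers per arm, ANCOVA changes power by -0.4 to +16 points. The gain is largest when baseline and 12-month SDs are similar and their correlation is low, and about zero when rho is close to r. ANCOVA does not guarantee 85%: it gives 84.4% at rho = r = 0.5 if 13.7 is the SD of change, and about 83 to 84% in the imputed set near there.

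The imputation model matters more. Across the scenarios simulated, power with arm out is 47 to 90% (change score) or 60 to 92% (ANCOVA), against 75 to 98% and 83 to 98% with arm in.

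These figures rest on assumed rho and r, both readings of the 13.7 min SD, 40 of 140 missing completely at random and equally by arm, and arm being absent from the primary imputation model. For H2 to H4 no figure is possible, since the document gives no difference or SD for them; only the variance inequality carries over. Confidence is medium.

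**What to change.** Amend the SAP before outcome data are examined:
- Make the primary analysis of H1 to H4 an ANCOVA of the 12-month value on arm, with the baseline value of the same measure as covariate, at two-sided 0.05, on the multiply imputed intention-to-treat set, without adherence measures.
- Name arm and that baseline value as variables in the primary imputation model.
- Keep the change-score t-test, on the same imputed data, as a supportive analysis.

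If outcome data have already been examined, keep the t-test as primary and report the ANCOVA as a labelled sensitivity analysis. The document is dated 8/13/2019 and does not say which situation applies.

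Two clarifications are needed under either analysis: whether 13.7 min is the SD of 12-month values or of changes, and which of the two baseline constant-load tests supplies the baseline value.

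The cost is one dated amendment, one degree of freedom and about 1% of variance.
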